12. INTRAOCULAR PRESSURE (IOP)

Intraocular pressure will be measured by qualified study site personnel at each specified visit using a Goldmann applanation tonometer affixed to a slit lamp and in accordance with the site's standard practice. [REDACTED]

13. DILATED OPHTHALMOSCOPY

Dilated ophthalmoscopy will be performed at each specified visit.

The Investigator's preferred diagnostic dilating drop should be used and examination will be performed once the subject's eyes are deemed sufficiently dilated in the opinion of the Investigator. [REDACTED]

[REDACTED] cup-to-disc ratio will be recorded horizontally and vertically, and reported in 0.1 increments. The following will be examined:

- Vitreous
- Retina
- Macula
- Choroid
- Optic Nerve
- Cup-to-Disc

All findings should be recorded with appropriate medical terminology avoiding colloquialisms and abbreviations.

APPENDIX 3: GENERAL INSTRUCTIONS FOR COMPLETION OF SAE FORMS

1. As soon as possible, and at the latest within 24 hours of becoming aware of event, complete an initial SAE Form. The SAE Form must be completed with a black ink ball point pen, in English and with block capitals to facilitate the readability of the submitted document. Please ensure that all sections have been completed.
2. Evaluate the events of trial subjects and record on the case report form a diagnosis (when possible and appropriate) rather than each individual sign and symptom.
3. Terms such as death, hospitalization or a procedural name are not acceptable event terms.
 - Example: Subject was hospitalized for cholecystectomy due to cholecystitis. The event term would be "Cholecystitis" (not the procedure).
 - Example: "Death" is an outcome not an event term. The Investigator should report the primary cause of death as the SAE term.
4. All initial SAE reports must have the relationship to study medication documented.
5. All SAEs will be:
 - Followed to resolution (subject's health has returned to their baseline status or all variables have returned to normal) or
 - Followed until stabilization of the event has occurred (the Investigator does not expect any further improvement or worsening of the event) or
 - The event is followed up to 30 days after last study medication application.
 - Some events do not end, such as metastasis; however, once these events are determined by the Principal Investigator to be stable or chronic, the PI may consider the event to be resolved or resolved with sequelae.
6. In case of death:
 - Specify the cause of death (do not use the term "death" and avoid using cardiac arrest or respiratory failure if possible. Instead, provide the diagnosis leading to cardiac arrest or respiratory failure.)
 - There should be only one SAE with an outcome of death for each subject.
 - For other adverse events that were ongoing at the time of death, enter outcome of these events as 'Ongoing.'
 - Please submit a copy of the Death Certificate and Autopsy Report (if applicable).
7. Review all source documents (examples - hospital discharge summary, hospital notes) as additional SAEs may be detected. If there are any questions as to whether you think an additional SAE may be present, please contact the Medical Monitor to discuss.
8. Protect the subject's identity. Redact all individually identifiable information (e.g., subject's name, medical record number, social security number and any parent or spouse

information such as names and addresses) in the header as well as in the body of the text on any supporting documents.

9. Follow-up SAE form completion instructions:

- Complete and submit further Follow-up Reports for data collected until the SAE has resolved or a decision for no further follow up has been taken.
- Complete a new SAE Form. At the top of the first page, tick the follow-up report or final report box and fax all pages even if changes were only made to one of the pages
- Retain the submission confirmation.

10. In case of mistake on the original initial SAE Form submitted to the SAE contact person, correct it, date and sign it and submit it again. Retain the submission confirmation.

11. Downgrading/deletion of a previously reported SAE:

If the Investigator determines a previously reported SAE doesn't meet serious criteria, a Follow-up SAE report should be completed. Document in the "Event Summary" section a brief explanation of why the Investigator determined the event to not be serious (*i.e.*, "it was determined that the subject was not hospitalized; therefore, this event does not meet serious criteria" or "the event was determined to be past medical history")

12. File original forms in the Case Report Form (CRF) of the subject.

13. Inform the IRB per IRB requirements and as required by local regulations.

APPENDIX 4: SUBJECT'S DOSING INSTRUCTIONS

The first eyelid scrub and study medication application will be performed at Baseline/Day 1 Visit at the site under the supervision of the study staff. At the Day 4, 8, 11 and 14 Visits, eyelid scrub and morning study medication administration will be also performed under the supervision of the study staff.

**Eyelid Scrub Instructions**

1. Wash your hands thoroughly with soap and water.

Preparation of diluted baby shampoo solution:

Now proceed with performing the eyelid scrub beginning with the right eye:

6. 

IMPORTANT! THE COTTON SWAB MUST NOT MAKE CONTACT WITH THE SURFACE OF THE EYE OR THE WHITE PART OF THE EYE. The only contact should be to the specified areas of the eyelid.

You must apply the study medication as instructed below using the supplies provided by the study site.

If you have been instructed by study staff to apply study medication *once daily*, you will apply the medication in the morning [REDACTED]

If you have been instructed by study staff to apply study medication *twice daily*, you will apply the medication in the morning [REDACTED]

[REDACTED], AND you will apply the medication in the evening [REDACTED] after washing your face.

Study Medication Application Instructions

1. Wash your hands thoroughly with soap and water.

Preparation of study medication:

2. [REDACTED]

[REDACTED]

[REDACTED]

[REDACTED]

[REDACTED]

[REDACTED]

[REDACTED]

[REDACTED]

Now proceed with applying the study medication beginning with the right eye:

10. [REDACTED]

[REDACTED]

[REDACTED]

IMPORTANT! THE APPLICATOR SPONGE MUST NOT MAKE CONTACT WITH THE SURFACE OF THE EYE OR THE WHITE PART OF THE EYE. The only contact should be to the specified areas of the eyelid.

12.2 Treatment Exposure.....	18
13 Efficacy Analyses	19
13.1 [REDACTED]	
13.2 Efficacy Endpoints.....	19
13.3 Eyelid Assessments	20
13.3.1 [REDACTED]	
[REDACTED]	
[REDACTED]	
13.3.4 Composite Score of Eyelid Margin Redness, Eyelid Debris, and Eyelid Discomfort.	21
13.4 Detailed Description of the Efficacy Analysis.....	21
13.4.1 [REDACTED]	
[REDACTED]	
[REDACTED]	
[REDACTED]	
[REDACTED]	
14 [REDACTED]	
[REDACTED]	
[REDACTED]	
[REDACTED]	
[REDACTED]	
[REDACTED]	
[REDACTED]	
15 Safety Analyses	25
15.1 Adverse Events	25
15.2 Best Corrected Visual Acuity.....	27
15.3 Intraocular Pressure.....	28
15.4 Slit Lamp Biomicroscopy Examination.....	28
16 Interim Analyses.....	28
17 Changes from Protocol Stated Analyses	28
18 References	28

19	Revision History	28
20	Tables to Be Included In the Final Analysis	29
21	Listings	35
22	Appendix A.....	37

List of Abbreviations

AE	Adverse Event
ANOVA	Analysis of Variance
ATC	Anatomical Therapeutic Chemical
BCVA	Best Corrected Visual Acuity
BID	Bis In Die (Twice Daily)
CI	Confidence Interval
Ecrf	Electronic Case Report Form
ETDRS	Early Treatment of Diabetic Retinopathy Study
GEE	Generalized Estimating Equations
ICH	International Conference on Harmonisation
IOP	Intraocular Pressure
ITT	Intent-to-Treat
logMAR	Logarithm of the Minimum Angle of Resolution
MedDRA	Medical Dictionary for Regulatory Activities
OD	Oculus Dextrus (Right Eye)
PDF	Portable Document Format
PP	Per Protocol
PT	Preferred Term
QD	Quaque Die (Once Daily)
RTF	Rich Text Format
SAE	Serious Adverse Event
SAP	Statistical Analysis Plan
SD	Standard Deviation
SDC	Statistics & Data Corporation
SEM	Standard Error of the Mean
SOC	System Organ Class
TEAE	Treatment-Emergent Adverse Event
WHO	World Health Organization

1 Introduction

The purpose of this statistical analysis plan (SAP) is to describe the planned analyses and reporting for protocol NCX-4251-01, version 5.0 dated 13 Aug 2019. [REDACTED]

[REDACTED]

[REDACTED]

[REDACTED]

[REDACTED]

[REDACTED]

[REDACTED] the combined analyses for Cohort 1 and Cohort 2 analysed together will be covered in the body of this “Final Statistical Analysis Plan for NCX 4251-01 Phase 2 Clinical Study” and carried out following database lock and unmasking of the Cohort 2 portion of the NCX 4251-01 study.

This SAP is being written with due consideration of the recommendations outlined in the most recent International Conference on Harmonisation (ICH) E9 Guideline, titled Guidance for Industry: Statistical Principles for Clinical Trials, and the most recent ICH E3 Guideline, titled Guidance for Industry: Structure and Content of Clinical Study Reports.

This SAP describes the data that will be analyzed and the subject characteristics, efficacy, and safety assessments that will be evaluated. This SAP provides details of the specific statistical methods that will be used. The statistical analysis methods presented in this document will supersede the statistical analysis methods described in the clinical protocol. If additional analyses are required to supplement the planned analyses described in this SAP, they may be completed and will be identified in the clinical study report.

2 Study Objectives

Primary Objective

The primary objective of this clinical study is to select the dose(s) of NCX 4251 to be advanced into the next stage of development.

Secondary Objectives

The secondary objectives of the study are to assess the safety and tolerability of the study medication applied once daily (QD) and twice daily (BID).

2.1 Study Variables

The following will be collected in the course of the study:

- Eyelid signs and symptoms (Eyelid Debris, Eyelid Margin Redness, and Eyelid Discomfort)
- [REDACTED]
- [REDACTED]
- [REDACTED]

- Intraocular pressure (IOP)
- Dilated ophthalmoscopy
- Best-corrected visual acuity (BCVA)
- Urine pregnancy tests (for females of childbearing potential)
- Adverse Events (AE)

5.45 - 5.50	100
5.50 - 5.55	100
5.55 - 5.60	100
5.60 - 5.65	100
5.65 - 5.70	100
5.70 - 5.75	100
5.75 - 5.80	100
5.80 - 5.85	100
5.85 - 5.90	100
5.90 - 5.95	100
5.95 - 6.00	100
6.00 - 6.05	100
6.05 - 6.10	100
6.10 - 6.15	100
6.15 - 6.20	100
6.20 - 6.25	100
6.25 - 6.30	100
6.30 - 6.35	100
6.35 - 6.40	100
6.40 - 6.45	100
6.45 - 6.50	100
6.50 - 6.55	100
6.55 - 6.60	100
6.60 - 6.65	100
6.65 - 6.70	100
6.70 - 6.75	100
6.75 - 6.80	100
6.80 - 6.85	100
6.85 - 6.90	100
6.90 - 6.95	100
6.95 - 7.00	100
7.00 - 7.05	100
7.05 - 7.10	100
7.10 - 7.15	100
7.15 - 7.20	100
7.20 - 7.25	100
7.25 - 7.30	100
7.30 - 7.35	100
7.35 - 7.40	100
7.40 - 7.45	100
7.45 - 7.50	100
7.50 - 7.55	100
7.55 - 7.60	100
7.60 - 7.65	100
7.65 - 7.70	100
7.70 - 7.75	100
7.75 - 7.80	100
7.80 - 7.85	100
7.85 - 7.90	100
7.90 - 7.95	100
7.95 - 8.00	100
8.00 - 8.05	100
8.05 - 8.10	100
8.10 - 8.15	100
8.15 - 8.20	100
8.20 - 8.25	100
8.25 - 8.30	100
8.30 - 8.35	100
8.35 - 8.40	100
8.40 - 8.45	100
8.45 - 8.50	100
8.50 - 8.55	100
8.55 - 8.60	100
8.60 - 8.65	100
8.65 - 8.70	100
8.70 - 8.75	100
8.75 - 8.80	100
8.80 - 8.85	100
8.85 - 8.90	100
8.90 - 8.95	100
8.95 - 9.00	100
9.00 - 9.05	100
9.05 - 9.10	100
9.10 - 9.15	100
9.15 - 9.20	100
9.20 - 9.25	100
9.25 - 9.30	100
9.30 - 9.35	100
9.35 - 9.40	100
9.40 - 9.45	100
9.45 - 9.50	100
9.50 - 9.55	100
9.55 - 9.60	100
9.60 - 9.65	100
9.65 - 9.70	100
9.70 - 9.75	100
9.75 - 9.80	100
9.80 - 9.85	100
9.85 - 9.90	100
9.90 - 9.95	100
9.95 - 10.00	100
10.00 - 10.05	100
10.05 - 10.10	100
10.10 - 10.15	100
10.15 - 10.20	100
10.20 - 10.25	100
10.25 - 10.30	100
10.30 - 10.35	100
10.35 - 10.40	100
10.40 - 10.45	100
10.45 - 10.50	100
10.50 - 10.55	100
10.55 - 10.60	100
10.60 - 10.65	100
10.65 - 10.70	100
10.70 - 10.75	100
10.75 - 10.80	100
10.80 - 10.85	100
10.85 - 10.90	100
10.90 - 10.95	100
10.95 - 11.00	100
11.00 - 11.05	100
11.05 - 11.10	100
11.10 - 11.15	100
11.15 - 11.20	100
11.20 - 11.25	100
11.25 - 11.30	100
11.30 - 11.35	100
11.35 - 11.40	100
11.40 - 11.45	100
11.45 - 11.50	100
11.50 - 11.55	100
11.55 - 11.60	100
11.60 - 11.65	100
11.65 - 11.70	100
11.70 - 11.75	100
11.75 - 11.80	100
11.80 - 11.85	100
11.85 - 11.90	100
11.90 - 11.95	100
11.95 - 12.00	100
12.00 - 12.05	100
12.05 - 12.10	100
12.10 - 12.15	100
12.15 - 12.20	100
12.20 - 12.25	100
12.25 - 12.30	100
12.30 - 12.35	100
12.35 - 12.40	100
12.40 - 12.45	100
12.45 - 12.50	100
12.50 - 12.55	100
12.55 - 12.60	100
12.60 - 12.65	100
12.65 - 12.70	100
12.70 - 12.75	100
12.75 - 12.80	100
12.80 - 12.85	100
12.85 - 12.90	100
12.90 - 12.95	100
12.95 - 13.00	100
13.00 - 13.05	100
13.05 - 13.10	100
13.10 - 13.15	100
13.15 - 13.20	100
13.20 - 13.25	100
13.25 - 13.30	100
13.30 - 13.35	100
13.35 - 13.40	100
13.40 - 13.45	100
13.45 - 13.50	100
13.50 - 13.55	100
13.55 - 13.60	100
13.60 - 13.65	100
13.65 - 13.70	100
13.70 - 13.75	100
13.75 - 13.80	100
13.80 - 13.85	100
13.85 - 13.90	100
13.90 - 13.95	100
13.95 - 14.00	100
14.00 - 14.05	100
14.05 - 14.10	100
14.10 - 14.15	100
14.15 - 14.20	100
14.20 - 14.25	100
14.25 - 14.30	100
14.30 - 14.35	100
14.35 - 14.40	100
14.40 - 14.45	100
14.45 - 14.50	100
14.50 - 14.55	100
14.55 - 14.60	100
14.60 - 14.65	100
14.65 - 14.70	100
14.70 - 14.75	100
14.75 - 14.80	100
14.80 - 14.85	100
14.85 - 14.90	100
14.90 - 14.95	100
14.95 - 15.00	100
15.00 - 15.05	100
15.05 - 15.10	100
15.10 - 15.15	100
15.15 - 15.20	100
15.20 - 15.25	100
15.25 - 15.30	100
15.30 - 15.35	100
15.35 - 15.40	100
15.40 - 15.45	100
15.45 - 15.50	100
15.50 - 15.55	100
15.55 - 15.60	100
15.60 - 15.65	100
15.65 - 15.70	100
15.70 - 15.75	100
15.75 - 15.80	100
15.80 - 15.85	100
15.85 - 15.90	100
15.90 - 15.95	100
15.95 - 16.00	100
16.00 - 16.05	100
16.05 - 16.10	100
16.10 - 16.15	100
16.15 - 16.20	100
16.20 - 16.25	100
16.25 - 16.30	100
16.30 - 16.35	100
16.35 - 16.40	100
16.40 - 16.45	100
16.45 - 16.50	100
16.50 - 16.55	100
16.55 - 16.60	100
16.60 - 16.65	100
16.65 - 16.70	100
16.70 - 16.75	100
16.75 - 16.80	100
16.80 - 16.85	100
16.85 - 16.90	100
16.90 - 16.95	100
16.95 - 17.00	100
17.00 - 17.05	100
17.05 - 17.10	100
17.10 - 17.15	100
17.15 - 17.20	100
17.20 - 17.25	100
17.25 - 17.30	100
17.30 - 17.35	100
17.35 - 17.40	100
17.40 - 17.45	100
17.45 - 17.50	100
17.50 - 17.55	100
17.55 - 17.60	100
17.60 - 17.65	100
17.65 - 17.70	100
17.70 - 17.75	100
17.75 - 17.80	100
17.80 - 17.85	100
17.85 - 17.90	100
17.90 - 17.95	100
17.95 - 18.00	100
18.00 - 18.05	100
18.05 - 18.10	100
18.10 - 18.15	100
18.15 - 18.20	100
18.20 - 18.25	100
18.25 - 18.30	100
18.30 - 18.35	100
18.35 - 18.40	100
18.40 - 18.45	100
18.45 - 18.50	100
18.50 - 18.55	100
18.55 - 18.60	100
18.60 - 18.65	100
18.65 - 18.70	100
18.70 - 18.75	100
18.75 - 18.80	100
18.80 - 18.85	100
18.85 - 18.90	100
18.90 - 18.95	100
18.95 - 19.00	100
19.00 - 19.05	100
19.05 - 19.10	100
19.10 - 19.15	100
19.15 - 19.20	100
19.20 - 19.25	100
19.25 - 19.30	100
19.30 - 19.35	100
19.35 - 19.40	100
19.40 - 19.45	100
19.45 - 19.50	100
19.50 - 19.55	100
19.55 - 19.60	100
19.60 - 19.65	100
19.65 - 19.70	100
19.70 - 19.75	100
19.75 - 19.80	100
19.80 - 19.85	100
19.85 - 19.90	100
19.90 - 19.95	100
19.95 - 20.00	100
20.00 - 20.05	100
20.05 - 20.10	100
20.10 - 20.15	100
20.15 - 20.20	100
20.20 - 20.25	100
20.25 - 20.30	100
20.30 - 20.35	100
20.35 - 20.40	100
20.40 - 20.45	100
20.45 - 20.50	100
20.50 - 20.55	100
20.55 - 20.60	100
20.60 - 20.65	100
20.65 - 20.70	100
20.70 - 20.75	100
20.75 - 20.80	100
20.80 - 20.85	100
20.85 - 20.90	100
20.90 - 20.95	100
20.95 - 21.00	100
21.00 - 21.05	100
21.05 - 21.10	100
21.10 - 21.15	100
21.15 - 21.20	100
21.20 - 21.25	100
21.25 - 21.30	100
21.30 - 21.35	100
21.35 - 21.40	100
21.40 - 21.45	100
21.45 - 21.50	100
21.50 - 21.55	100
21.55 - 21.60	100

2.5 Statistical Hypotheses

There are no formal hypotheses in this early phase study.

3 Study Design and Procedures

3.1 General Study Design

This is a multi-center, randomized, double-masked, placebo-controlled, dose-escalation study consisting of two cohorts, Cohort 1 and Cohort 2 studied sequentially. Each cohort consists of two arms, placebo and NCX 4251 Ophthalmic Suspension 0.1%. Approximately 15 subjects in Cohort 1 will be randomized in a 2:1 ratio (NCX 4251:placebo) and will receive study medication QD. [REDACTED]

[REDACTED] Approximately 20 subjects in Cohort 2 will be randomized in a 1:1 ratio and will receive study medication BID. Screening of eligible subjects for Cohort 2 will commence after the interim analysis from the Cohort 1 is conducted.

In each cohort, subjects will be assessed for initial eligibility at the Screening Visit (Day -7 to -3). Eligible adult subjects with a history of blepharitis and who are experiencing an acute exacerbation of blepharitis defined as a minimum score of '1' (on a 4-point scale) for each of Eyelid Margin Redness, Eyelid Debris, and overall Eyelid Discomfort [REDACTED] at both the Screening and Baseline/Day 1 Visits will be randomized into the study.

For both Cohorts 1 and 2, study visits will be as follows: Screening (Day -7 to -3), Baseline/Day 1, Day 4 (\pm 1 day), Day 8 (\pm 1 day), Day 11 (\pm 1 day), Day 14 (- 1 day; last day of treatment), and Day 28/Exit (\pm 2 days; follow-up visit).

Following the Screening Visit prior to Baseline/Day 1 Visit, subjects will continue their previous routine for cleaning of eyelids that they were using prior to Screening Visit. Both eyes will be treated from the Baseline/Day 1 Visit through Day 14 Visit. The study eye will be the eye with the highest composite score before eyelid scrubs at Baseline/Day 1 or the right eye (OD) if both eyes of a subject have the same score at baseline. The contralateral eye will be considered as the fellow eye. After the Day 14 Visit, subjects will continue using the eyelid scrubs per instructions provided in the study protocol until the day prior to the Day 28/Exit Visit.

Study medication will be self-administered topically in the morning (Cohort 1), or in the morning and evening (Cohort 2). Morning eyelid scrubs and morning study medication application will be performed by the subject at the clinical site on the days of study visits under supervision of the study personnel.

A subject will be considered as having completed the study after completion of Day 28/Exit Visit (\pm 2 days). The duration of subject participation (from the Screening Visit to the Exit Visit) is approximately 5 weeks.

The overall study duration is estimated to be approximately 6 months from the first subject enrolled until completion of the last subject.

The study design is essentially identical for Cohort 1 and Cohort 2; the main differences are the dosing frequency (QD vs. BID), the randomization ratio (2:1 vs 1:1), [REDACTED]

3.2 Schedule of Visits and Assessments

The schedule of visits and assessments is provided in Appendix A.

4 Study Treatments

4.1 Method of Assigning Subjects to Treatment Groups

At the Screening Visit, subjects who provide verbal and written informed consent will be assigned a unique 5-digit subject ID, which consists of the 2-digit site number plus a unique 3-digit screening number (beginning with 001 within each site). A subject must meet all qualification criteria at the Baseline/Day 1 Visit to be randomized. Approximately 15 subjects in Cohort 1 will be randomly assigned to NCX 4251 0.1% QD or placebo QD in a 2:1 ratio. Approximately 20 subjects in Cohort 2 will be randomly assigned to NCX 4251 0.1% BID or placebo BID in a 1:1 ratio. Study drug will be randomly assigned using a (2:1 for Cohort 1, 1:1 for Cohort 2) assignment ratio, which is stratified by site. Sequentially numbered study drug kits will be provided to each investigational site, in accordance with the site-specific randomized study drug kit list, which consists of sequential 4-digit kit ID numbers. Subjects who meet all eligibility criteria will be randomized by assignment of the lowest 4-digit study drug kit number available at their investigational site. If a randomized subject is discontinued from the study for any reason, their randomized study drug kit number will not be reassigned. A back-up block of treatments will be available at each site to be used for study treatment replacement.

The 5-digit subject ID will be used to identify subjects in all datasets and listings for this study.

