4. SUBJECT SELECTION

4.1 Number of Subjects and Sites

This study will be conducted at approximately 3 to 5 sites in the U.S. Additional sites may be added based on enrollment rates. Overall, approximately 50 subjects will be screened and 35 subjects will be randomized into the study.

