APPENDIX 2: METHODS OF CLINICAL EVALUATION

For all assessments, sites should use the same instrument(s), method and examiner whenever possible throughout the study. All ophthalmic assessments will be performed bilaterally. The right eye will be assessed first, then the left eye.

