7.2 Per Protocol

The per-protocol (PP) population includes subjects in the ITT population who do not have significant protocol deviations likely to seriously affect the efficacy measures of the study. Protocol deviations will be assessed prior to database lock and unmasking. Subjects in the PP population will be analyzed as treated. The t-test analyses on the composite score of eyelid margin redness, eyelid debris, and eyelid discomfort will be conducted using the PP population as an additional analysis to assess efficacy when subjects strictly comply with the protocol. In the event that the ITT and PP populations are the same, this analyses will not be performed.

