[REDACTED]. Summaries for continuous variables will include the number of observations (n), arithmetic mean, standard deviation (SD), standard error of the mean (SEM), median, minimum, and maximum. Minima and maxima will be reported with the same precision as the raw values; means and medians will be presented to one additional decimal place than reported in the raw values. Standard deviations and standard errors of the mean will be presented to two additional decimal places than reported in the raw values. Summaries for discrete and ordinal efficacy (Eyelid Margin Redness, Eyelid Debris, and Eyelid Discomfort, along with the composite score) variables will include frequency counts and percentages. All percentages will be rounded to one decimal place (i.e., XX.X%). For continuous variables, the differences between active treatment groups and placebo will be calculated as Active – Placebo using descriptive statistics and two-sample Student's t-distribution CIs and p-values. Within one group, change from baseline will be calculated as Follow-up Visit – Baseline using descriptive statistics and one-sample Student's t-distribution CIs and p-values; differences in mean change from baseline scores between treatment groups will be summarized including 95% t-distribution CIs around the differences in mean. Summaries will be presented for each post-baseline visit. These summaries will be completed separately for the pre-scrub and post-scrub assessments. For discrete variables, binomial proportions and Clopper-Pearson CIs will be used to compare follow-up visit to baseline within each treatment group; Fisher's Exact Test will be used to compare the categorical endpoints between treatment groups.

All assessments will be summarized by study eye, fellow eye, and by both eyes, unless specifically stated. When the assessments need to be presented in both eyes, for continuous variables, between group CIs and p-values will come from a mixed effects linear model for each post-baseline visit

Confidence intervals (CI) for differences between treatment groups will be two-sided at 95% confidence. P-values may also be presented for change from baseline values, however the study is not powered to show significance for these.

Unless otherwise specified, summaries will be presented by treatment group and, where appropriate, visit.

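### Randomisation is stratified by site, but the readable study-eye comparison of the composite is a two-sample t interval without site or baseline; if sites differ in change, precision is lost and the planning SD includes between-site variance.

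*SAP*

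**What the plan says.** **Design.** SAP 4.1 specifies an "assignment ratio, which is stratified by site", 2:1 in Cohort 1 and 1:1 in Cohort 2, with site-specific kit lists. Protocol 4.1 says: "This study will be conducted at approximately 3 to 5 sites in the U.S". Planned sizes are about 10 v 5 (Cohort 1) and 10 v 10 (Cohort 2).

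**Analysis.** The general convention in SAP 8.4 is that "differences in mean change from baseline scores between treatment groups will be summarized including 95% t-distribution CIs around the differences in mean". SAP 7.2 names the method for the composite when it plans the per-protocol repeat: "The t-test analyses on the composite score of eyelid margin redness, eyelid debris, and eyelid discomfort will be conducted using the PP population". Protocol 11.5.2 describes the same kind of interval. None of the readable text puts site or baseline into these comparisons, and SAP 17 (changes from protocol-stated analyses) does not mention site.

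**Both eyes.** Here "between group CIs and p-values will come from a mixed effects linear model for each post-baseline visit", but the readable text stops before the model's terms. Much of SAP 13.4 is blacked out.

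**Measurement.** Redness and debris are graded by the investigator and discomfort by the subject, each from 0 to 3 (SAP 13.3). Protocol Appendix 2 asks that "sites should use the same instrument(s), method and examiner whenever possible throughout the study".

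**Purpose.** There are no formal hypotheses (SAP 2.5) and no power target. SAP 5 says the sample size is meant to help obtain estimates for powering future studies.

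**The concern.** Stratifying by site balances the arms within site, which largely removes site differences from the treatment contrast. A plain two-sample t interval takes no credit for this. Its pooled SD still contains whatever part of the outcome variance lies between sites, so the stated uncertainty is larger than the design delivers.

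The endpoint is change from baseline, so what counts is whether sites differ in change. Plausible sources in this trial are:

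- grader drift, or a switch of examiner (the same-examiner instruction applies only where possible);
- case mix;
- scrub technique, which each site's staff teach and supervise (protocol 7.2 to 7.5);
- the floor of the scale. Entry needs at least 1 on each of three items scored 0–3 (SAP 3.1), so the baseline composite runs from 3 to 9 and a subject cannot improve by more than the baseline value. A site that grades higher leaves more room to fall.

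The last point also argues for a baseline term.

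At stake are the width of the intervals and the SD carried into the next trial. That SD is one of the study's main products.

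**Working it through.** **1. Figures in the plan.** The readable text gives no SD, effect size, interval width or site variance, so there is no stated figure to reproduce. Results below are in units of the total SD of change, over an assumed range of site shares.

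**2. Unadjusted half-width.** The formula is t(0.975, N−2) × SD × √(1/n₁ + 1/n₀), using the planned sizes and two-sided 95% intervals (SAP 8.4).

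- Cohort 2, 10 v 10: 2.101 × √(0.1 + 0.1) = 0.94 SD.
- Cohort 1, 10 v 5: 2.160 × √(0.1 + 0.2) = 1.18 SD.

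**3. Cost of a site term alone.** With 3 to 5 sites it uses 2 to 4 df.

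- Cohort 2: t rises from 2.101 (18 df) to 2.120–2.145 (16 to 14 df), or +0.9% to +2.1%.
- Cohort 1: t rises from 2.160 (13 df) to 2.201–2.262 (11 to 9 df), or +1.9% to +4.7%.

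**4. Net effect on width.** The t interval was compared with a linear model of treatment plus fixed site effects in 6,000 simulated trials per setting. Assumptions not in the documents: near-equal site sizes, 3 or 5 sites, blocks of 2 or 4 (Cohort 2) or 3 (Cohort 1), and normal outcomes. The site share is the fraction of the variance of change that lies between sites. Ranges run over numbers of sites and block sizes.

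| Assumed site share | Adjusted ÷ unadjusted width, Cohort 2 | Same, Cohort 1 | Coverage of the unadjusted 95% interval |
|---|---|---|---|
| 0 | 1.01–1.02 | 1.03–1.04 | about 95% |
| 5% | 0.99–1.00 | 1.01–1.02 | 95.3–95.7% |
| 10% | 0.97–0.98 | 0.99 | 95.6–96.1% |
| 20% | 0.92–0.94 | 0.93–0.95 | 96.0–96.9% |
| 30% | 0.87–0.89 | 0.88–0.90 | 96.8–97.6% |
| 50% | 0.75–0.79 | 0.76–0.79 | 97.5–98.7% |

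Coverage of the adjusted interval stays at about 95% throughout.

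**5. Reading at 20%.** The ratios 0.92–0.95 invert to 1/0.95 = 1.05 and 1/0.92 = 1.09, so the unadjusted interval is about 5–9% wider. The simpler SE ratio, 1/√0.8 = 1.12, is larger because it ignores the lost df and imperfect balance within sites.

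**6. Break-even.** In Cohort 1 the ratio crosses 1 between shares of 5% and 10%; linear interpolation gives about 7–8%. In Cohort 2 it crosses just under 5% (interpolated 3.5–4.4%), and at 5% the gain is still below 1% (ratios 0.994–0.998). So about 4–5% is a fair working threshold there.

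**7. Cost of the full model** (arm, site, baseline). Baseline adds 1 df, for a total of 3 to 5.

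- Four arms, 35 subjects: t(31) = 2.040 becomes t(28) = 2.048 to t(26) = 2.056, or +0.4% to +0.8%.
- Cohort 1 fitted alone: t(13) = 2.160 becomes t(10) = 2.228 to t(8) = 2.306, or +3.1% to +6.7%.

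The gain from the baseline term was not quantified, because the documents give no correlation between baseline and change.

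**The case against.** The strongest reply is that the endpoint already deals with grader differences. A consistently harsh or lenient examiner shifts baseline and follow-up alike, and the offset subtracts out; the same-examiner instruction helps this. Discomfort is rated by the subject. A low site share of change is therefore plausible, and near zero share adjustment makes the interval 1–4% wider. All of this stands, and it makes the point conditional. It does not make the share zero, for the reasons listed under the concern.

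Second, site or baseline may enter analyses that cannot be read. The mixed-model sentence is cut off, SAP 13.4 is largely blacked out, and the abbreviation lists include ANOVA and GEE (SAP) and ANCOVA (protocol). This also stands. A reader might infer that every between-arm interval ignores site; the documents show this only for the readable t analyses.

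Third, the total SD is the right planning value if the later trial is analysed without site. That is correct, so both SDs should be reported.

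Fourth, with about five Cohort 1 placebo subjects over 3 to 5 sites, some sites may have one or none. This argues for one model on all subjects and a pooling rule, with the t interval retained. It does not show the t interval alone to be the better choice.

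**Conclusion.** The point holds as a minor, conditional one. The design stratifies by site and the readable study-eye analysis of the composite uses neither site nor baseline. If sites differ in change, the t interval is conservative: about 5–9% too wide at an assumed 20% site share, with coverage of 96.0–96.9%. If the share is below about 4–5% (Cohort 2) or 7–8% (Cohort 1), site adjustment alone gains nothing. These sizes rest on the assumed site shares, near-equal sites and assumed block sizes.

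Three stronger readings are not supported:

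- That the intervals are too wide as a matter of fact. No site variance is given.
- That site grading differences in general remain in the error term. Stable ones mostly cancel in change.
- That omitting site biases the estimate or inflates type I error. The error is on the conservative side. Chance imbalance within sites under randomisation is not bias, and no block size is readable from which to judge it.

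With no hypotheses and no power target, the consequence is limited to precision and the SD used for planning.

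**What to change.** For the study-eye composite, add to the SAP active-minus-placebo estimates with 95% intervals from one linear model on all randomised subjects with observed data. Its terms would be treatment arm (four levels), site and baseline composite. Set the rule for pooling very small sites before unmasking. Report both the residual SD and the total SD of change, so that a later trial can be planned with or without site in its analysis. Keep the plain t interval beside the model estimate, and state for every model, including the both-eyes one, whether site enters.

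Stratification was done separately within each cohort, so a single site term assumes that a site behaves alike in both. The SAP should say so.

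The cost is SAP wording and one more table, plus 3 to 5 degrees of freedom: about 0.4–0.8% on the t multiplier in the four-arm model, or about 3–7% if Cohort 1 were fitted alone. No new data are needed, since site and baseline score are already collected.
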